5.2 Exclusion Criteria

Subjects are excluded from the study if any of the following criteria apply:

- 201 History of other malignancy within the past 2 years, with the following exceptions:
- Malignancy treated with curative intent and with no known active disease present for ≥ 2 years before enrollment and felt to be at low risk for recurrence by the treating physician
 - Adequately treated non-melanoma skin cancer or lentigo maligna without evidence of disease.
 - Adequately treated non-muscle invasive urothelial carcinoma
- 202 History or presence of hematological malignancies unless curatively treated with no evidence of disease ≥ 2 years
- 203 Untreated (includes new lesions or progression in previously treated lesions) or symptomatic brain metastases and leptomeningeal disease
- 204 History or presence of relevant CNS pathology such as uncontrolled epilepsy or seizure disorder, aphasia, paresis, dementia, severe brain injuries, Parkinson's disease, cerebellar disease, organic brain disorder, or psychosis
- 205 Myocardial infarction within 12 months of study day 1, symptomatic congestive heart failure (New York Heart Association > class II), unstable angina, or clinically significant uncontrolled cardiac arrhythmia
- 206 History of arterial thrombosis (eg, stroke or transient ischemic attack) within 12 months of first dose of tarlatamab

- 207 Has a diagnosis of immunodeficiency or is receiving systemic steroid therapy (prednisone dose > 10 mg per day or equivalent dose) or any other form of immunosuppressive therapy within 7 days prior study day 1
- 208 Active autoimmune disease requiring systemic treatment within the past 2 years **of study day 1** (ie, with the use of disease modifying agents, non-physiologic doses of corticosteroids or immunosuppressive drugs); including current autoimmune sequelae or previous Grade > 2 autoimmune sequelae from checkpoint inhibitors or other immunomodulatory treatments that require systemic therapy
- Exception: Participants with autoimmune endocrine disorders on hormonal supplementation may be enrolled even if > Grade 2 when it first occurred, if approved by the Medical Monitor.
- 209 Presence of fungal, bacterial, viral, or other infection requiring oral or IV antimicrobials for management within 7 days of first dose tarlatamab.
- Note: Simple UTI and uncomplicated bacterial pharyngitis are permitted if responding to active treatment and after consultation with sponsor. Subjects requiring oral antibiotics who have been afebrile > 24 hours, have no leukocytosis or have any clinical signs of infection are eligible. Subjects who meet these criteria and who were previously on IV antimicrobials should have been off IV antimicrobials for > 48 hours.
- 210 Exclusion of hepatitis infection based on the following results and/or criteria:
- Positive Hepatitis B Surface Antigen (HepBsAg) (indicative of chronic Hepatitis B or recent acute hepatitis B).
 - Negative HepBsAg and positive for hepatitis B core antibody: hepatitis B virus DNA by polymerase chain reaction (PCR) is necessary. Detectable hepatitis B virus DNA suggests occult hepatitis B.
 - Positive Hepatitis C virus antibody: Hepatitis C virus RNA by PCR is necessary. Detectable Hepatitis C virus RNA suggests chronic hepatitis C.
- 211 Known positive test for human immunodeficiency virus (HIV)
- 212 Anti-tumor therapy within 28 days of study day 1; concurrent use of hormone deprivation therapy for hormone-refractory prostate is permitted; subjects on a stable bisphosphonate or denosumab for ≥ 30 days prior to study day 1 are eligible
- Exceptions:
 - Subjects who received conventional chemotherapy are eligible if at least 14 days have elapsed and if all treatment-related toxicities have resolved to Grade ≤ 1
 - Prior palliative radiotherapy must have been completed at least 7 days before the first dose of tarlatamab
 - Subjects who received androgen signaling inhibitor (eg, abiraterone, enzalutamide, and/or apalutamide) are eligible if at least 14 days have elapsed and if all treatment-related toxicity has been resolved to Grade ≤ 1
- 213 Major surgical procedures ≤ 28 days or non–study-related minor procedures ≤ 7 days prior to study day 1. In all cases, the subjects must be sufficiently recovered and stable before treatment administration

- 214 Currently receiving treatment in another investigational device or drug study, or less than 28 days **from study day 1** since ending treatment on another investigational device or drug study(ies). Other investigational procedures while participating in this study are excluded with the exception of

- 215 Unresolved toxicities from prior anti-tumor therapy, defined as not having resolved to Common Terminology Criteria for Adverse Events (CTCAE) version 4.0 grade 1, or to levels dictated in the eligibility criteria with the exception of alopecia or toxicities that are stable and well-controlled and there is agreement to allow by the investigator and sponsor
- 216 Subject unable to receive both iodinated contrast for CT scans and gadolinium contrast for magnetic resonance imaging (MRI) scans
- 217 Subject has known sensitivity and immediate hypersensitivity to any components of tarlatamab
- 218 Subject likely to not be available to complete all protocol-required study visits or procedures, and/or to comply with all required study procedures to the best of the subject and investigator's **awareness**
- 219 History or evidence of any other clinically significant disorder, condition or disease (with the exception of those outlined above) that, in the opinion of the investigator or Amgen physician, if consulted, would pose a risk to subject safety or interfere with the study evaluation, procedures, or completion
- 220 Male subjects with a female partner of childbearing potential who are unwilling to practice sexual abstinence (refrain from heterosexual intercourse) or use contraception during treatment and for **60** days after the last dose of tarlatamab. Refer to Section 11.5 for additional contraceptive information.
- 221 Male subjects with a pregnant partner who are unwilling to practice abstinence or use a condom during treatment and for **60** days after the last dose of tarlatamab.
- 222 Male subjects unwilling to abstain from donating sperm during treatment and for **60** days after the last dose of tarlatamab.
- 223 Subjects on prior DLL3-targeted therapy may be eligible if discussed with Amgen medical monitor prior to enrollment
- 224 History of hypophysitis or pituitary dysfunction
- 225 Has evidence of interstitial lung disease or active, non-infectious pneumonitis.
- 226 Live and live-attenuated vaccines within 4 weeks prior to study drug administration.
- 227 History or evidence of SARS-COV2 infection unless agreed upon with Medical Monitor and with no acute symptoms of COVID19 disease within 14 days prior to first dose of IP (counted from day of positive test for asymptomatic subjects).

5.3 Subject Enrollment

Before subjects begin participation in any study-specific activities/procedures, Amgen requires a copy of the site's written **external review bodies** approval of the protocol,

informed consent form (ICF), and all other subject information and/or recruitment material, if applicable (see Section [11.3](#)).

The subject or legally authorized representative must personally sign and date the **external review bodies (eg, the institutional review board [IRB]/independent ethics committee[IEC]/regulatory authorities)** and Amgen approved informed consent before commencement of study-specific procedures.

A subject is considered enrolled when the investigator decides that the subject has met all eligibility criteria. The investigator is to document this decision and date, in the subject's medical record and in/on the enrollment case report form (CRF).

Each subject who enters into the screening period for the study (defined as the point at which the subject or legally authorized representative signs the informed consent) receives a unique subject identification number before any study-related activities/procedures are performed. The subject identification number will be assigned manually. This number will be used to identify the subject throughout the clinical study and must be used on all study documentation related to that subject.

The subject identification number must remain constant throughout the entire clinical study; it must not be changed after initial assignment, including if a subject is rescreened.

5.4 Screen Failures

Screen failures are defined as subjects who consent to participate in the clinical study but are not subsequently enrolled in the study. A minimal set of screen failure information will be collected that includes demography, screen failure details, eligibility criteria, medical history, prior therapies, and any serious adverse events.

Individuals who do not meet the criteria for participation in this study (screen failure) may be rescreened one time at the investigator's decision. Refer to Section [8.1.1](#).

6. Treatments

Study treatment is defined as any investigational product(s), noninvestigational product(s), placebo, or medical device(s) intended to be administered to a study subject according to the study protocol.

Note that in several countries, investigational product and noninvestigational product(s) are referred to as investigational medicinal product and noninvestigational product(s)/auxiliary, respectively.

The Investigational Product Instruction Manual (IPIM), a document external to this protocol, contains detailed information regarding the storage, preparation, destruction, and administration of each treatment shown in [Table 6-1](#) below.

6.1 Treatment(s) Administered

6.1.1 Investigational Products

Table 6-1. Study Treatments

Amgen Investigational Product:^a	
Study Treatment Name	Tarlatamab
Dosage Formulation	Tarlatamab is supplied as a sterile, single use, preservative free lyophilized drug product containing [REDACTED] mg of tarlatamab per vial. Tarlatamab is intended for reconstitution with sterile water for injection and dilution in an IV bag with normal saline ([REDACTED] sodium chloride) and an IV solution stabilizer. The drug product is formulated with L-glutamic acid, sucrose, polysorbate 80, pH [REDACTED]
Unit Dose Strength(s)/ Dosage Level(s) and Dosage Frequency	At the time of initiation of the study, the starting dose will be the highest dose deemed safe and tolerable in the ongoing phase 1 trial of tarlatamab in subjects with small cell lung cancer (Note: based on emerging safety data from Study 20160323, the starting dose may be lower than the highest dose deemed safe and tolerable).
Route of Administration	Tarlatamab will be administered as a short-term IV infusion for 60 minutes followed by a flush once every 2 weeks (with step-dosing).
Accountability	The date, time, package lot number, dose, and the start and stop time of infusion are to be recorded on the individual subject's Investigational Product Administration CRF.
Dosing Instructions	Tarlatamab will be administered at the study center by a qualified staff member. A physician must be available at the time of administration of investigational products. Please refer to IPIM for more details on dosage, administration, and schedule of tarlatamab.

CRF = case report form; IPIM = Investigational Product Instruction Manual; IV = intravenous.

^a Tarlatamab will be manufactured and packaged by Amgen Inc. and distributed using Amgen clinical study drug distribution procedures.

6.1.2 Medical Devices

Investigational medical devices will not be used in this study.

Other noninvestigational medical devices may be used in the conduct of this study as part of standard care.

Noninvestigational medical devices (eg, syringes, sterile needles), that are commercially available are not usually provided or reimbursed by Amgen (except, for example, if required by local regulation). The investigator will be responsible for obtaining supplies of these devices.

6.1.3 Noninvestigational Product(s)/Auxiliary Medicinal Product(s)

All **noninvestigational product(s)/auxiliary medicinal product(s)** including, dexamethasone and normal saline, that are commercially available are not provided or reimbursed by Amgen (except if required by local regulation). The investigator will be responsible for obtaining supplies of these **noninvestigational product(s)/auxiliary medicinal product(s)**. Due to the mechanism of action of tarlatamab, CRS and neurological events are important potential risks. Corticosteroid has been used for prophylaxis and treatment of CRS and neurological events secondary to blinatumomab and other BiTE[®] molecules.

Prophylaxis with IV hydration 1 L normal saline over 4 to 5 hours immediately following all dose(s) in cycle 1 is required.

Dexamethasone 8 mg IV (or equivalent dose of other corticosteroids) will be administered within 1 hour prior to each dose of tarlatamab in cycle 1.

Dexamethasone dose and schedule may be changed based on emerging safety data.

6.1.4 Other Treatment Procedures

Sites are required to have tocilizumab or siltuximab (if tocilizumab not available) on site for potential treatment of CRS.

6.1.5 Product Complaints

A product complaint is any written, electronic or oral communication that alleges deficiencies related to the identity, quality, durability, reliability, safety, effectiveness, or performance of a drug, combination product, or device after it is released for distribution to market or clinic by either (1) Amgen or (2) distributors or partners for whom Amgen manufactures the material. This includes all components distributed with the drug, such as packaging drug containers delivery systems, labeling, and inserts.

This includes any investigational product (tarlatamab) provisioned and/or repackaged/modified by Amgen.

Any product complaint(s) associated with an investigational product supplied by Amgen are to be reported.

6.1.6 Excluded Treatments, Medical Devices, and/or Procedures During Study Period

The following treatments and/or procedures are excluded within the timeframes specified during the study:

- Other investigational agents
- Concurrent experimental or approved anti-tumor therapies other than study drugs
- Radiation therapy
 - Exception: Radiation therapy for symptom control (eg, bone metastasis) or brain metastases may be allowed after discussion with the Medical Monitor. The radiation therapy should not include the thoracic field and must have been completed at least 7 days before the subsequent dose of tarlatamab
- Chronic systemic corticosteroid therapy (prednisone dose > 10 mg per day or equivalent) or any other immunosuppressive agents with the exception of those required by protocol, treatment for adverse events, CNS metastases, corticosteroid replacement therapy or unless agreed upon by the principal investigator (PI) and Medical Monitor
- Any live vaccine therapies. Examples of live vaccines include, but are not limited to, the following: measles, mumps, rubella, chicken pox, yellow fever, rabies, Bacillus Calmette–Guérin (BCG), and typhoid (oral) vaccine. Seasonal influenza vaccines for injection are generally killed virus vaccines and are allowed. However, intranasal influenza vaccines (eg, Flu-Mist[®]) are live attenuated vaccines, and are not allowed
- Subjects must not schedule any major elective surgery during the treatment period and for at least 30 days after the last administration of study drugs. If a subject undergoes any unexpected surgery during the course of the study, all study treatments must be withheld, and the investigator or designee should notify the sponsor's medical monitor as soon as possible. A subject may be allowed to resume study drugs if both the investigator and sponsor's medical monitor agree to restart study therapy.

6.2 Dose Modification

6.2.1 Dose-cohort Study Escalation/De-escalation and Stopping Rules

6.2.1.1 Dose Level Review Team

For the dose exploration phase, a DLRT will convene to review the safety data before recommendations to dose escalate. The required DLRT voting members include the Medical Monitor, Global Safety Officer (GSO), and Site Investigator or designee. The DLRT members are responsible for dosing recommendations, which may include

implementing step dosing, escalation to the next dose, de-escalation to a lower dose, exploring intermediate dose levels; continuation, delay or termination of dosing; or repetition or expansion of a cohort; or determination of MTD or RP2D. The DLRT will not make dose escalation recommendations until at least 3 subjects enrolled at the dose level are deemed DLT-evaluable. Cumulative adverse events profile will be taken into consideration when making recommendations on dose escalation or de-escalation. See Section 11.3 for more details regarding the DLRT.

6.2.1.2 Dose-cohort Study Escalation

Details on dose-cohort study escalation and stopping rules will refer to Section 4.1.

6.2.1.2.1 Dose Limiting Toxicity

Dose-limiting toxicity (DLT) is defined as any qualifying toxicity that is at least possibly related to tarlatamab with an onset within the first 28 days following first dose with either of the following criteria:

- Grade 3 adverse event lasting more than 3 days (with the exception of fatigue and Grade 3 non-febrile neutropenia that improves to \leq Grade 1 within 3 weeks including the use of growth factor support per neutropenia management guidelines [see Section 6.8.6]);
- \geq Grade 4 adverse event regardless of duration (with the exception of grade 4 non-febrile neutropenia lasting less than or equal to 7 days including the use of growth factor support per neutropenia management guidelines [see Section 6.8.6]).

Laboratory parameters of Grade 4, not considered clinically relevant and improved to Grade \leq 2 within 72 hours, will not be considered DLT's.

Asymptomatic grade 4 electrolyte abnormalities that last $<$ 72 hours, are not clinically complicated, and resolve spontaneously or respond to conventional medical interventions will not be considered DLTs.

The following adverse events will NOT be adjudicated as DLT regardless of the grade or duration:

- Lymphopenia
- Fever
- Tumor lysis syndrome (TLS) including associated manifestations attributable to TLS (eg, electrolyte abnormalities, renal dysfunction, hyperuricemia)

6.2.2 Dosage Adjustments, Delays, Rules for Withholding or Restarting, Permanent Discontinuation

6.2.2.1 Amgen Investigational Product: Tarlatamab

The reason for dose change of tarlatamab is to be recorded on each subject's CRF.

6.2.2.1.1 Dosage Adjustment

Subjects should continue on the same target dose of tarlatamab (not including the initial run-in dose and step dose(s)) throughout the study. The two exceptions are subjects who meet criteria for intra-subject dose escalation (see Section 6.2.2.1.4 for more details) and subjects who experienced a DLT or other intolerable tarlatamab-related adverse events but showing evidence of clinical benefit. These subjects will have an option to reduce the dose to the immediate next lower dose level shown to be safe and tolerable in the dose exploration part of the study, after discussion with the Amgen Medical Monitor. The study drug can be resumed once the adverse events recover to Grade 0-1 and the reintroduction of tarlatamab is deemed safe by the investigator, Medical Monitor, and GSO. The subjects must be informed of the risk of continuing on therapy. Each subject is only allowed one dose reduction. For adverse events related to CRS, neurological events, and pituitary dysfunction, please see Sections 6.8.1, 6.8.2, and 6.8.3, respectively for guidelines for dose adjustments.

6.2.2.1.2 Dose Delays

During the first 28 days DLT observation period, if the dosing of tarlatamab is delayed for more than 72 hours for reasons other than DLT during the DLT evaluation period, a replacement subject may be enrolled and assigned to the same dose level. The subject may continue on study only after discussion with the Medical Monitor.

After the 28-day DLT observation period, if the dosing of tarlatamab is delayed for ≤ 2 weeks, the subject should resume the treatment as soon as possible if deemed safe by the investigator. The investigator should inform the Amgen Clinical team as soon as the unexpected dosing interruption occurs. If the dosing of tarlatamab is delayed between 2 to 4 weeks due to severe or life-threatening treatment-related adverse events, the subject can resume treatment if the toxicities resolve to grade ≤ 1 or return to subjects' baseline values within 4 weeks and restarting of therapy has been deemed safe by the investigator and medical monitor.

If the dosing of tarlatamab is delayed for more than 4 weeks due to severe or life-threatening treatment-related adverse events, the subject will be discontinued from investigational product (IP). If the dosing delay occurred under other conditions, the

case will be reviewed by the Sponsor to determine whether and when the subject will be allowed to resume tarlatamab.

For adverse events related to CRS, neurological events, and pituitary dysfunction, please see Sections 6.8.1, 6.8.2, and 6.8.3 respectively for guidelines for dose delays.

6.2.2.1.3 Rules for Withholding or Restarting

Tarlatamab should be withheld for any of the following:

- DLT
- Symptomatic hypophysitis (See Section 6.8.3)
- Criteria for conditional withholding of tarlatamab due to potential hepatotoxicity (Section 6.2.3)

Tarlatamab dosing can be resumed if the toxicities resolve to grade ≤ 1 or return to subjects' baseline values within 4 weeks. The restarting of therapy should be deemed safe by the investigator and medical monitor.

Subjects should not be restarted with tarlatamab if the following treatment-related adverse events occur:

- Any grade ≥ 4 adverse events except those not considered DLT as described in Section 6.2.1.2.2
- Grade 3 adverse event(s) that do not recover to Grade 0-1 within 4 weeks
- Any grade 3 adverse events that recur (with the exception of grade 3 laboratory parameters not considered clinically relevant or recurrent non-febrile grade 3 neutropenia which resolves with supportive care to grade ≤ 1 or returns to subjects' baseline values within 4 weeks)
- Criteria for permanent withholding of tarlatamab due to potential hepatotoxicity (Section 6.2.3)

For adverse events related to CRS, neurological events and pituitary dysfunction, please see Sections 6.8.1, 6.8.2, and 6.8.3 respectively for guidelines for withholding and restarting criteria to pause enrollment.

At any point during the study, enrollment will be paused at the occurrence of 2 or more Grade 4 or one or more Grade 5 IP related adverse events. DLRT will be reconvened to review the safety data and determine appropriate next step that may include but not limited to implementing safety/toxicity management, informing health authorities, voluntarily putting the clinical trial on hold, or proceeding with enrollment (note: following the occurrence of an enrollment pause and DLRT review, a subsequent enrollment pause will occur at the occurrence of 2 or more new Grade 4 or one or more Grade 5 IP

related adverse events; additionally, if a pause and a DLRT has already occurred and the appropriate safety/toxicity management for Grade 4 adverse events have already been implemented a subsequent enrollment pause may not occur).

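### Sections 6.2.2.1.1 and 6.2.2.1.2 permit re-dosing that the no-restart list in 6.2.2.1.3 bars, no sentence says which controls, and the list's Grade 4 exception cites a section that does not exist

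*Protocol*

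**What the plan says.** Three neighbouring subsections of the protocol govern re-dosing after toxicity.

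- **6.2.2.1.1 Dosage Adjustment** gives an option to "subjects who experienced a DLT or other intolerable tarlatamab-related adverse events but showing evidence of clinical benefit". They may move to the "immediate next lower dose level shown to be safe and tolerable in the dose exploration part of the study" after discussion with the Medical Monitor. Dosing resumes on recovery to Grade 0-1, provided "the reintroduction of tarlatamab is deemed safe by the investigator, Medical Monitor, and GSO". The subject must be told of the risk, and only one reduction is allowed. For CRS, neurological and pituitary events the section defers to 6.8.1 to 6.8.3.
- **6.2.2.1.2 Dose Delays** applies two resumption rules after the 28-day DLT period. After a delay of 2 weeks or less, dosing should resume if the investigator judges it safe, and the site informs the sponsor of the interruption. After 2 to 4 weeks' delay for severe or life-threatening related events, dosing can resume on recovery to Grade 1 or baseline within 4 weeks, with the investigator and Medical Monitor agreeing. A delay of more than 4 weeks for such events ends treatment.
- **6.2.2.1.3 Rules for Withholding or Restarting** requires withholding for a DLT, then states: "Tarlatamab dosing can be resumed if the toxicities resolve to grade" 1 or lower, or to baseline, within 4 weeks. A bar follows: "Subjects should not be restarted with tarlatamab if the following treatment-related adverse events occur". The list covers Grade 4 or higher "adverse events except those not considered DLT as described in Section 6.2.1.2.2", Grade 3 events not recovered to Grade 0-1 within 4 weeks, recurrent Grade 3 events (with stated exceptions), and the permanent hepatotoxicity criteria.

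The DLT definition is in Section 6.2.1.2.1. It counts any "Grade 4 adverse event regardless of duration", and higher grades, apart from short non-febrile neutropenia and other listed exclusions. It applies only to events "with an onset within the first 28 days following first dose".

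**The concern.** A DLT can be a Grade 4 event. The dose-reduction option is therefore open, on its wording, to subjects whom the no-restart list excludes. The dose-delay rules likewise allow resumption after day 28 without mentioning the list. Neither permissive section refers to 6.2.2.1.3, and 6.2.2.1.3 refers to neither of them.

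The exception to the Grade 4 bar adds a second difficulty. It sends the reader to a section number that is not in the protocol. Once the right section is found, its 28-day window raises the question of whether a later Grade 4 event is exempt simply because it cannot be a DLT. Treatment continues until progression, so later events are realistic.

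At stake is whether a subject who has had a related Grade 4 event is exposed again. The people making that decision should not have to infer whether a safety bar binds them.

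**Working it through.** No arithmetic applies. The check sets the rules side by side for related events that have no rule of their own elsewhere.

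| Related event | 6.2.2.1.1 | 6.2.2.1.2 | 6.2.2.1.3 list |
|---|---|---|---|
| Non-exempt Grade 4, onset by day 28 (a DLT), recovered, clinical benefit | May resume one level lower | Resumption rules start after day 28 | Barred |
| Non-exempt Grade 4, onset after day 28, recovered | May resume one level lower if intolerable and with benefit | May resume: up to 2 weeks on the investigator's judgement; 2 to 4 weeks with the Medical Monitor | Barred, if the exception means listed event types only |
| Grade 3 that recurs | May resume one level lower, once | Does not mention recurrence | Barred, apart from its stated exceptions |
| Grade 3 recovering only after 4 weeks | May resume one level lower; no time limit | Treatment ends if the delay for a severe or life-threatening event exceeds 4 weeks | Barred |

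**Which events remain.** Several Grade 4 events drop out because other sections settle them:

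- Grade 4 CRS: permanent discontinuation (Table 6-2).
- Grade 4 neurologic events: permanent discontinuation (Table 6-3).
- Grade 4 non-febrile neutropenia: over 7 days, permanent discontinuation (Table 6-4); 7 days or less, not a DLT under 6.2.1.2.1.
- Hepatic events: Section 11.7.4. Pituitary events: Section 6.8.3.
- Lymphopenia, fever, TLS, and the laboratory and electrolyte abnormalities that meet the stated conditions: not DLTs under 6.2.1.2.1.

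The 6.2.2.1.1 route also needs a lower dose shown safe in Part 1, and Section 4.1 allows Part 1 to be eliminated. Grade 5 is in the wording of the bar but restart cannot arise.

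**The reference.** The headings run from 6.2.1.2.1 straight to 6.2.2, so there is no 6.2.1.2.2. The Amendment 7 summary records removal of a former step-dosing Section 6.2.1.2.1, which probably explains the stale number.

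**The scope after day 28.** There are two readings of the exception:

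- *Narrow*: only the event types that 6.2.1.2.1 lists as not DLTs are exempt.
- *Wide*: any Grade 4 event with onset after day 28 is exempt, since it falls outside the DLT definition.

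Tables 6-2 to 6-4 stop treatment after the Grade 4 events they name with no onset window, which fits the narrow reading. The 2-to-4-week branch of 6.2.2.1.2 does not settle the matter. Its wording also covers Grade 3 events and exempt Grade 4 events, and Section 8.2.4.1.2 recognises that a CTCAE Grade 4 finding need not be life-threatening.

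**Size.** Section 2.2.2.3 reports Grade 4 neutropenia in 5 of 113 exposed subjects (5/113 = 4.4%), none febrile. By the rules above, those events fall outside the overlap. It reports no Grade 4 or higher CRS at its cutoff and gives no separate rate for other Grade 4 related events. The number of subjects affected therefore cannot be derived.

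**The case against.** The strongest answer is that the sections can be reconciled. A permission and a prohibition do not clash: a site that obeys the bar breaches neither. Section 6.2.2.1.3 is the one headed for restarting, its bar has no carve-out for dose-reduced subjects, and it has the same structure internally, first allowing resumption after a DLT and then limiting it. The option keeps content under the bar, since Grade 3 events lasting more than 3 days are DLTs. The wrong section number is clerical, because only one section lists events that are not DLTs.

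Much of this stands. The reconciled reading is available, and the intended target of the reference is easy to find. But the reading is not compelled. Section 6.2.2.1.1 can equally be read as a specific exception with its own safeguards: recovery, agreement of three parties, informing the subject, and one reduction. Nothing in the text chooses between the two.

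A reader might infer three stronger points that the documents do not support:

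- *That every Grade 4 event after day 28 is free to restart.* The listed event types and Tables 6-2 to 6-4 point the other way.
- *That the protocol leaves re-dosing after Grade 4 events generally open.* Most of the expected Grade 4 toxicities have their own rules, and 6.2.2.1.1 requires agreement beyond the site. Those safeguards do not extend to the 2-week branch of 6.2.2.1.2, which rests on the investigator's judgement.
- *That Table 9-2 gives a count.* Its rates, 0.10 to 0.30, are hypothetical, include Grade 5 and events with their own rules, and describe Part 2 only.

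**Conclusion.** The point holds as a minor one. For non-exempt related Grade 4 events, 6.2.2.1.1 and 6.2.2.1.2 permit what 6.2.2.1.3 bars. For Grade 3 events that recur or have not recovered within 4 weeks, the same is true of 6.2.2.1.1. The four-week gap is partly closed by the discontinuation rule in 6.2.2.1.2, and the recurrence gap is limited by the single permitted reduction. The exception's reference is wrong in the current text, and its scope after day 28 is mostly, but not expressly, settled in favour of the narrow reading.

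Few subjects should be affected, and the number is not estimable from the documents. That rests on taking the separate rules for CRS, neurologic, neutropenic, hepatic and pituitary events as controlling for those events. DLT counts and the MTD are unaffected: a subject with a DLT is evaluable under Section 9.3.1 whatever dosing follows. The consequence is for individual safety decisions, not for the dose-finding result.

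**What to change.** In the next amendment or a clarification letter:

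1. Add to 6.2.2.1.1 and 6.2.2.1.2: *subject to the no-restart list in Section 6.2.2.1.3*. This deals with the Grade 4 and the Grade 3 items together.
2. Change the reference in 6.2.2.1.3 from 6.2.1.2.2 to 6.2.1.2.1.
3. State in 6.2.2.1.3 that the exception covers only the event types listed in 6.2.1.2.1 as not DLTs, whatever the day of onset. If the sponsor intends other related Grade 4 events after day 28 to be eligible for restart, it should say so and give the conditions.

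The cost is one or two sentences and a section number. No new data, analysis or design change is needed.
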